7.13.1 Sponsor Responsibilities

- Determine whether the safety information meets the requirements for expedited reporting to the applicable regulatory authorities
- Prepare and submit the safety report to the applicable regulatory authorities
- Send all participating PIs a safety report and Investigator Safety Letter (i.e., Dear Investigator Letter) that will include a statement if there is or is not any significant new safety information that might influence the risk-benefit assessment of the IP and/or study device, sufficient to consider changes in product administration or overall conduct of the clinical investigation

7.13.2 Principal Investigator (PI) Responsibilities

- Forward a copy of the safety report and Investigator Safety Letter (i.e., Dear Investigator Letter) to their IRB/REB/EC as soon as practical in accordance with the governing policy and/or procedures
- Notify their IRB/REB/EC of safety information (i.e., SAEs, pregnancies, etc.) that occur at their clinical trial site in accordance with their local institutional policy

7.14 POST-TRIAL REPORTING REQUIREMENTS

Principal Investigators (PIs) are not obligated to actively seek AEs or SAEs beyond the clinical trial reporting period. However, if the PI becomes aware of an AE or SAE that occurs after the Completion or Termination Visit and the event is deemed by the PI to be probably or possibly related to the clinical trial treatment, the PI should promptly document and report the event to the Sponsor.

7.15 CLINICAL TRIAL DISCONTINUATION

The Sponsor reserves the right to discontinue the clinical trial at this site or at multiple sites for safety or administrative reasons at any time. In particular, a clinical trial site that does not recruit at a reasonable rate may be discontinued. Additionally, the clinical trial may be discontinued at any time by an IRB/REB/EC, the Sponsor, or a regulatory authority as part of their duties to ensure that clinical trial subjects are protected.

If the clinical trial is discontinued and/or the clinical trial site closed for any reason, an Inovio Representative will provide instructions regarding which device components should be returned to Inovio Pharmaceuticals, Inc., destroyed onsite and/or shipped to a destruction vendor. The PI should ensure that their site file documents are complete prior to archiving and provide copies of any requested documents to the Sponsor for its Trial Master File (TMF).

8 STATISTICAL CONSIDERATIONS

8.1 STATISTICAL AND ANALYTICAL PLAN

The Statistical Analysis Plan is contained in the sections that follow.

8.2 GENERAL CONSIDERATIONS

The statistical analysis of the data will be performed by Inovio Pharmaceuticals or its representative.

This is a single-arm, multi-center clinical trial in subjects with HPV-6- and/or HPV-11-associated recurrent respiratory papillomatosis (RRP). The primary objective is to evaluate safety. The primary endpoint is safety and tolerability as assessed by reported adverse events (AE) and serious adverse events (SAE). Secondary efficacy analyses include evaluation of frequency of RRP surgical interventions in the year following the first dose of investigational product, compared to the frequency in the year prior to Day 0 dosing, and changes in RRP Staging Assessment over time. Other secondary analyses concern cellular immunological measures, and tissue immunological measures.

8.3 STATISTICAL HYPOTHESES

No formal statistical hypothesis will be tested in this study.

8.4 ANALYTICAL POPULATIONS

The analysis populations will be the following.

The intention to treat (ITT) population includes all subjects who are eligible.

The modified intention to treat (mITT) population includes all subjects who receive at least one dose of INO-3107.

The per-protocol (PP) population comprises subjects who receive all doses of INO-3107 and have no protocol violations. Subjects excluded from the PP population will be identified and documented prior to locking of the trial database.

The safety analysis set includes all subjects who receive at least one dose of INO-3107.

8.5 DESCRIPTION OF STATISTICAL METHODS

8.5.1 Primary Analyses

The primary analyses for this trial are safety analyses of Treatment Emergent Adverse Events (TEAE) and clinically significant changes in safety laboratory parameters from baseline.

TEAEs are defined for this trial as any AEs that occur following Day 0 following administration of study drug (IM + EP), until 30 days following the last dose. All TEAEs will be summarized among the Safety Population by frequency. These frequencies will be presented overall, by system organ class and by preferred term, the percentage of subjects affected. Additional frequencies will be presented with respect to maximum severity and to strongest relationship to study treatment. Multiple occurrences of the same

AE will be counted only once following a worst-case approach with respect to severity and relationship to study treatment. All serious TEAEs will also be summarized as above.

The main summary of safety data will be based on TEAEs. For this summary, the frequency of preferred term events will be calculated along with 95% confidence intervals, using the exact method of Clopper-Pearson. Separate summaries will be based on events occurring within 7 days of any dose and regardless of when they occurred. AEs and SAEs that are not TEAEs or serious TEAEs will be presented in listings.

For AE data, partial start dates will be imputed to the date of treatment to conservatively report the event as treatment-emergent, whenever the portion of the date is consistent with that of the study treatment. Otherwise, it will be imputed to the earliest date consistent with the partial date. A completely missing onset date will be imputed as the day of treatment. Partial stop dates will be assumed to be the latest possible day consistent with the partial date.

AE duration will be calculated as (Stop Date – Start Date) + 1.

Laboratory response variables will be descriptively summarized per time point and as changes from baseline including 95% confidence intervals. Shifts from baseline according to the CTCAE will also be presented. Laboratory values considered clinically significant will be presented in listings.

All of the safety analyses will be conducted on the subjects in the safety analysis set.

Analyses will be summarized and presented by number of prior surgical interventions (≤ 2 , 3-5, and ≥ 6) and overall.

8.5.2 Secondary Analyses

8.5.2.1 EFFICACY

The frequency of RRP surgical interventions in the year following the first dose of investigational product, compared to the frequency in the year prior to Day 0 dosing, will be summarized descriptively using mean fold-change and a 95% t-distribution-based CI.

Changes in RRP Staging Assessment scores from baseline pre-dose to each post-dose evaluation will be analyzed. Median changes and associated 95% confidence intervals will be computed.

[REDACTED]

Intersurgical intervals will also be summarized.

Analyses will be summarized and presented by number of prior surgical interventions (≤ 2 , 3-5, and ≥ 6) and overall. Efficacy analysis using the mITT population will be conducted. The PP population will also be used for a supportive analysis.

8.5.2.2 IMMUNOGENICITY

Increases from baseline in interferon- γ ELISpot and flow response magnitudes will be summarized. The median increases and associated 95% confidence intervals will be calculated.

Changes from baseline in tumor tissue response magnitudes will be summarized.

[REDACTED]

Valid samples for statistical analysis purposes will be those collected within 7 days of the specified visit. Baseline is defined as the last measurement prior to the first treatment administration.

The mITT population will be used for immunogenicity analyses.

Analyses will be summarized and presented by number of prior surgical interventions (≤ 2 , 3-5, and ≥ 6) and overall.

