10. As determined by the Investigator, have any medical or psychological or non-medical condition that might interfere with the subject's ability to participate or affect the safety of the subject.

Clinical Trial Treatment:

Subjects will receive a 1 mL injection of INO-3107 IM followed by EP. Doses will be administered at Day 0, Weeks 3, 6, and 9.

Device: CELLECTRA® 2000.

SCHEDULE OF EVENTS

Schedule of Events	Screening	Day 0	Week 3 (±4 days)	Week 6 (±4 days)	Week 9 (±4 days)	Week 11 (±1 week)	Week 26 (±2 week)	Week 52 /End of study (±2 weeks)
Informed consent	X							
Medical history, smoking history	X							
Inclusion/Exclusion criteria	X	X						
Demographics	X							
Concomitant medications, AEs	X	X	X	X	X	X	X	X
Physical exam ^a	X	X	X	X	X		X	X
Vital signs	X	X	X	X	X		X	X
Height, weight, BMI		X	X	X	X			
Safety labs ^b	X	X	X	X	X			
Pregnancy test, if applicable ^c	X	X	X	X	X			
INO-3107		X	X	X	X			
Immunology samples	X	X		X	X	X	X	X
Laryngoscopy and Staging assessment ^e	X ^f			X		X	X	X
Tissue sample ^g	X							X

- Full physical examination (PE) mandatory at screening and study discharge (Week 52/End of Study visit or relapse), otherwise targeted physical assessment as determined by the Investigator or per subject complaints.
- Collected within 72 hours prior to dosing such that results are available and assessed against DLT criteria prior to dosing.
- For women of childbearing potential, a negative serum pregnancy test is required at screening and a negative spot urine pregnancy test is required prior to each study treatment.
- Staging assessment to be performed during each laryngoscopy and prior to any RRP intervention using the RRP Staging Assessment tool. Video/photographic documentation of laryngoscopy is required.
- Staging to be performed prior to Routine RRP intervention at Screening, followed by dosing within 14 days.
- Biopsy tissue should be sent for HPV typing and immunological evaluation at Screening, Week 52, and at any tissue resection, if applicable. Archival tissue collected within 1 year of Day 0 may be sent at screening. Biopsy required with laryngoscopy at Week 52.

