6.1.2 CLINICAL TRIAL EVALUATIONS AND PROCEDURES

Once eligibility has been confirmed, the subject's Day 0 dose will be scheduled within 14 days after the next planned surgical intervention. If timing allows, the Day 0 dose may be given on the same day immediately following the next planned surgical intervention. Visit dates and windows must be calculated from Day 0, unless otherwise noted. All subjects will be followed until the Week 52 visit. All subjects will be followed per assessments outlined below.

6.1.2.1 Day 0

The following evaluations will be performed on Day 0 **prior to IP administration**:

- Collect all present and/or new or ongoing adverse events;
- Document any present conditions and concomitant illnesses;
- Record current concomitant medications/treatments ([Section 6.13](#));
- Targeted physical examination ([Section 6.4.1](#));
- Record vital signs ([Section 6.4.2](#));
- Record body weight, height and determine BMI ([Section 6.4.3](#));
- Collect urine for urine pregnancy test, if applicable ([Section 6.4.4](#));
- Collect whole blood [REDACTED] for immunology assessment ([Section 6.10](#));

- Collect safety labs within 72 hours prior to dosing such that results are available and assessed against DLT criteria prior to dosing ([Section 6.4.4](#));

The following evaluations will be performed on Day 0 **after IP administration**:

- Collect any new adverse events;
- Download EP Data ([Section 6.5.1](#)).

6.1.2.2 Week 3

The following evaluations will be performed at this visit **prior to IP administration**:

- Collect all present and/or new or ongoing adverse events;
- Document any present conditions and concomitant illnesses;
- Record current concomitant medications/treatments ([Section 6.13](#));
- Targeted physical examination ([Section 6.4.1](#));
- Record vital signs ([Section 6.4.2](#));
- Record body weight, height and determine BMI ([Section 6.4.3](#));
- Safety labs collected within 72 hours prior to dosing such that results are available and assessed against DLT criteria prior to dosing ([Section 6.4.4](#));
- Collect urine for urine pregnancy test, if applicable ([Section 6.4.4](#)).

The following evaluations will be performed **after IP administration**:

- Collect any new adverse events;
- Download EP Data ([Section 6.5.1](#)).

6.1.2.3 Week 6

The following evaluations will be performed **prior to IP administration**:

- Collect all present and/or new or ongoing adverse events;

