6.10 PERIPHERAL BLOOD IMMUNOGENICITY ASSESSMENTS

Whole blood [REDACTED] samples will be obtained at baseline (screening and Day 0 prior to dosing) and at Weeks 6, 9, 11, 26 and 52. Details of the immunology sample collection and shipment information will be provided in the Laboratory Manual.

PBMCs will be isolated from whole blood samples. [REDACTED]

[REDACTED]

[REDACTED]

[REDACTED]

[REDACTED]

[REDACTED]

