3.11. Visit Windows

Once eligibility has been confirmed, the subject's Day 0 dose will be scheduled within 14 days after the next planned surgical intervention. If timing allows, the Day 0 dose may be given on the same day immediately following the next planned surgical intervention. Visit dates and windows must be calculated from Day 0, unless otherwise noted. All subjects will be followed until the Week 52 visit.

It is expected that all visits should occur according to the protocol schedule. All data will be tabulated per the scheduled visit as recorded on the case report form (CRF) even if the assessment is unscheduled (outside of the visit window). For example, a visit that occurs after the scheduled Week 6 visit, but before the scheduled Week 9 visit, will be reported (tabulated) with the Week 6 data. In data listings, the relative day of all dates will be presented.

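### Immunology sample validity (protocol) and by-visit filing (SAP) follow incompatible rules, and the SAP rule lets pre-surgery Staging scores or resected tissue enter the Week 26 summary up to 181 days late

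*Protocol*

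**What the plan says.** **Sample validity.** Protocol 8.5.2.2 (Immunogenicity) states: "Valid samples for statistical analysis purposes will be those collected within 7 days of the specified visit". It does not say whether the specified visit is the target date or the visit as held. Protocol 6.1.2 states: "Visit dates and windows must be calculated from Day 0, unless otherwise noted".

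**Visit windows.** The Schedule of Events gives ±4 days at Weeks 6 and 9, ±1 week at Week 11 and ±2 weeks at Week 26. The final column reads "Week 52 /End of study (±2 weeks". Immunology samples are marked at all five visits. Protocol 6.10 confirms that blood "samples will be obtained at baseline (screening and Day 0 prior to dosing) and at Weeks 6, 9, 11, 26 and 52".

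**Tabulation.** SAP 3.11 (Visit Windows) states: "All data will be tabulated per the scheduled visit as recorded on the case report form (CRF) even if the assessment is unscheduled". It explains unscheduled as meaning outside the visit window. Its example concerns an attendance between two planned ones: "visit that occurs after the scheduled Week 6 visit, but before the scheduled Week 9 visit, will be reported (tabulated) with the Week 6 data". SAP 4.3.2 calls for median increases with 95% CIs at each assessment point and does not repeat the 7-day rule.

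**Assessments between visits.** A Schedule of Events footnote reads: "Staging assessment to be performed during each laryngoscopy and prior to any RRP intervention using the RRP Staging Assessment tool". Another footnote asks for tissue at any resection.

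**Declared changes.** The visible entries in SAP Section 5 cover the switch to a median change for surgical frequency and the 21-subject subset analysis. A redacted item follows.

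**The concern.** There are two separate problems.

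1. **Which samples count.** One document excludes samples by distance from the visit and the other keeps everything. Programmers working from different documents could produce different Week 26 and Week 52 immune-response tables, and immune response is a named secondary endpoint. Analyses use observed data only (protocol 8.5.7), so an excluded sample is not replaced. The tables are also split into three prior-surgery groups (≤2, 3-5, ≥6) among about 30 subjects, so losing a few samples would matter.

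2. **What a by-visit row contains.** The SAP example has no limit on lateness, and no rule selects among several values under one visit label. Extra Staging scores are foreseeable because staging is required before every intervention, and eligibility requires at least two interventions in the prior year. These scores come only from subjects judged to need surgery, so their entry into a by-visit summary is related to outcome. Median Staging change is also a secondary endpoint.

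**Working it through.** The plan gives no figure to reproduce. The check is calendar arithmetic with day = 7 × week, counted from Day 0.

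**Step 1. Compliant dates outside 7 days, if the specified visit is the target date.**

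| Visit | Target day | Permitted days | Days permitted | More than 7 days off target |
|---|---|---|---|---|
| Week 6 | 42 | 38-46 | 9 | 0 |
| Week 9 | 63 | 59-67 | 9 | 0 |
| Week 11 | 77 | 70-84 | 15 | 0 |
| Week 26 | 182 | 168-196 | 29 | 14 (168-174, 190-196) |
| Week 52 | 364 | 350-378 | 29 | 14 (350-356, 372-378) |

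At Weeks 26 and 52, 14/29 = 48% of permitted days are compliant but invalid. This is a share of calendar days, not of samples. If the specified visit means the visit as held, the count is 0 everywhere.

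**Step 2. Share of samples, under assumed timing.** The documents give no data on actual visit dates. Assume that the deviation from target is normal with mean 0 and standard deviation s, limited to ±14 whole days, with a half-day continuity correction:

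share lost = 1 − [2Φ(7.5/s) − 1] / [2Φ(14.5/s) − 1]

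For s = 5: 2Φ(1.5) − 1 = 0.866 and 2Φ(2.9) − 1 = 0.996, so the share lost is 1 − 0.866/0.996 = 0.13.

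| Assumed SD (days) | Share of compliant samples lost | Of 30 subjects |
|---|---|---|
| 3 | 1% | 0.4 |
| 5 | 13% | 3.9 |
| 7 | 26% | 7.7 |
| 10 | 36% | 10.8 |

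The answer depends almost wholly on the assumed SD.

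**Step 3. Longest delay under the SAP example.** Apply the example to each pair of consecutive visits in Step 1. The latest day still filed under a visit is the day before the next target.

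- Week 6: 62 − 42 = 20 days
- Week 9: 76 − 63 = 13 days
- Week 11: 181 − 77 = 104 days
- Week 26: 363 − 182 = 181 days, about 26 weeks

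These are maxima measured from target dates. With an early Week 26 visit (day 168) and a late Week 52 visit (day 378), the gap between actual dates can reach 377 − 168 = 209 days.

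**Step 4. Which data each rule touches.** Blood immunology is drawn only at scheduled visits, so Step 3 hardly affects it. Step 3 mainly concerns pre-surgery Staging scores, tissue from unscheduled resections, and any repeat safety labs.

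**Step 5. After the fix.** With the Schedule of Events windows as the validity rule, 0 of 29 permitted days are excluded at Weeks 26 and 52. In a summary restricted to in-window records, no Week 26 value is more than 14 days from target.

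**The case against.** **The two rules do not operate together.** If SAP 3.11 governs, no compliant sample is lost, and SAP version 2.0 (December 2022) is later than protocol version 4.0 (July 2021). A tighter analysis window also costs sample size without being an error in itself. This stands. A reader might infer that both rules produce wrong by-visit results, but the documents do not support that. They show a conflict that has not been visibly reconciled. The later date does not resolve it, because protocol 8.1 presents its own Section 8 as the statistical analysis plan.

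**The loss depends on an undefined term.** If the specified visit is the visit as held, nothing compliant is excluded. This stands as a condition. The Day 0 anchor in protocol 6.1.2 favours the target date but does not settle it.

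**Section 5 may already cover the change.** A redacted item follows the visible entries, so it cannot be said that the change is undeclared, only that no visible entry declares it.

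**SAP 3.11 may only mean that a late scheduled visit keeps its CRF label.** That is a fair reading of the parenthesis, and listings will show relative days. But the rule covers all data, and the example places a visit between two scheduled ones under the earlier label. Nothing separates a late scheduled visit from an additional assessment, and no rule handles several values under one label.

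**These are secondary, descriptive summaries with no hypothesis test.** True, and it limits the weight of the point. By-visit medians with CIs will still be read as results.

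**Conclusion.** The point holds in limited form. The protocol's 7-day rule and SAP 3.11 cannot both be followed at Weeks 26 and 52. On the target-date reading, 14 of 29 permitted days at each visit yield compliant but excluded samples. The number of samples affected is unknown, about 1% to 36% under timing SDs that are assumptions. Weeks 6, 9 and 11 are unaffected.

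The SAP example has a separate defect. As written, a required pre-surgery Staging score, or resected tissue, obtained between Weeks 26 and 52 can be summarised as Week 26, at most 181 days after target and only for subjects who needed surgery.

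Two stronger readings are tempting and should be resisted. A reader might infer that blood immune responses are mislabelled by half a year, but blood is drawn only at scheduled visits. A reader might also infer that Week 26 would look worse and Week 52 better by comparison. That direction is not established: no duplicate rule is stated, and by the same logic scores between Weeks 11 and 26 would fall under Week 11.

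**What to change.** (a) State in SAP 3.11, and record in Section 5, that the 7-day rule of protocol 8.5.2.2 is superseded and that scheduled immunology samples within the Schedule of Events windows are valid.

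(b) State that by-visit summaries use one record per subject per visit, namely the scheduled-visit record. A scheduled visit held outside its window keeps its CRF visit label and is flagged. Add a sensitivity summary restricted to in-window records.

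(c) State that unscheduled assessments, including pre-surgery Staging scores, unscheduled tissue and repeat labs, are listed or summarised separately and are not carried back into the preceding visit's summary.

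The cost is a few sentences in the SAP and a little extra programming, with no new data. The downside is that unscheduled values no longer contribute to the by-visit tables.

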8.5.3 Disposition

Disposition will be summarized and will include the number and percentage eligible, the number and percentage who received each dose and the number who completed the trial. The number and percentage of subjects who discontinued will be summarized overall and by reason. The number in each analysis population will also be presented.

Analysis will be summarized and presented by number of prior surgical interventions (≤ 2 , 3-5, and ≥ 6) and overall.

8.5.4 Demographic and Other Baseline Characteristics

8.5.4.1 DEMOGRAPHICS

Demographic and baseline characteristic data will be summarized with descriptive statistics: mean standard deviation, minimum, median, and maximum values for continuous variables, and percentages for categorical variables, for the ITT population.

Analysis will be summarized and presented by number of prior surgical interventions (≤ 2 , 3-5, and ≥ 6) and overall.

8.5.4.2 PRIOR MEDICATION

Prior medications are those that were used before the start of the trial (prior to Day 0). Partial stop dates of prior medications will be assumed to be the latest possible date consistent with the partial date; start dates will not be imputed. Data for all prior medications will be summarized with percentages for the mITT population.

Analyses will be summarized and presented by number of prior surgical interventions (≤ 2 , 3-5, and ≥ 6) and overall.

